to accurately "phenotype" lumbar spine surgery patients for relevant trait and state constructs associated with centralized pain. *Hypothesis 1a: Pre-operative patient characteristics associated with a centralized pain phenotype will be associated with and potentially predict a patient's failure to derive benefit from surgery intended to treat chronic pain. Hypothesis 1b: Patients who fail to obtain pain relief from lumbar spine surgery in a longitudinal cohort will appear phenotypically similar to a cross-sectional cohort of established-FBSS patients and those who do obtain pain relief from lumbar spine surgery will appear phenotypically similar (except for back pain) to healthy controls.*

Aim 2: To confirm that altered pain processing mechanisms consistent with centralized pain are seen in patients who have failed to respond to lumbar spine surgery. In order to accomplish this aim, the candidate will learn how to perform and analyze the results of quantitative sensory testing (QST) (detecting pain thresholds, testing the integrity of descending analgesic pathways, and temporal summation). *Hypothesis 2a: Pre-operative altered pain processing mechanisms consistent with centralized pain will be associated with and potentially predict a patient's failure to derive benefit from surgery intended to treat chronic pain. Hypothesis 2b: Patients who fail to obtain pain relief from lumbar spine surgery in a longitudinal cohort will have augmented QST changes similar to a cross-sectional cohort of established-FBSS patients and those who do obtain pain relief from lumbar spine surgery will have QST changes similar to healthy controls.*

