
C. Sample size, statistical methods, and power calculation

Aim 1 Analyses: To demonstrate that common patient characteristics consistent with a centralized pain phenotype are associated with a patient's failure to derive benefit from lumbar spine surgery. **Analysis**

1a: Analgesic outcomes (AOC) for patients in the prospective cohort will be defined as "AOC-success" or "AOC-failure" for the purposes of further analyses. AOC-success is defined as those who demonstrate a 50% reduction in pain scores from baseline to 6 months, which would be a response more commensurate with the invasiveness of the intervention of spine surgery than a minimal clinically important difference score (MCID). FMness as measured by the 2011 FM Survey Criteria score⁶⁶ is the primary measure of interest and will be split by median score (and defined as FM-high and FM-low). Differences in surgical failure proportions (determined by pain score change as described above at 6-months) between the FM-high (n=50) and FM-low (n=50) groups will be tested using a two-sided chi-squared statistic at $\alpha=.05$. In addition to FMness, differences between AOC-success and AOC-failure groups for each of the constructs contained under the subheading "Comprehensive Phenotyping Battery" will be examined using appropriate parametric or non-parametric analyses. Furthermore, we wish to explore how multiple patient characteristics vary across these cohorts. A stepwise logistic regression model will then be fit to evaluate multivariate relationships. The analyses conducted in this aim will provide the candidate an opportunity to learn multivariate data analysis with advanced regression modeling as well as more familiarity with patient reported outcome measures. **Analysis 1b:**

Phenotypic differences between the AOC-failure group and the established-FBSS group will be examined using appropriate parametric or non-parametric tests to see if the longitudinally designated AOC-failure cohort is phenotypically similar in nature to the cross-sectional established-FBSS patients. We hypothesize that AOC-failure patients will appear similar to established-FBSS patients. The same comparisons will be explored for the longitudinally designated AOC-success group compared to the cross-sectional healthy controls group.

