Aim 2 Analyses: To confirm that altered pain processing mechanisms consistent with centralized pain are seen in patients who have failed to respond to lumbar spine surgery. Pain thresholds, cuff algometry, CPM, and temporal summation scores will be treated as continuous measures and normality will be assessed prior to analysis. The same analyses as those conducted for Aim 1 will be used for this aim.

Aim 3 Analyses: To investigate whether structural, functional, and chemical brain imaging provides evidence of the neurobiological signature for centralized pain in patients who fail to derive benefit from lumbar spine surgery. AFNI, BrainVoyager, LCMoel, FSL, MatLab, SPM, and Freesurfer will be used for functional MRI, structural MRI, and spectroscopy MR analyses based on the analytical methods previously described by [name] and his research colleagues.^{54,58,74,76,122,131-141} **Analysis 3a:** Pre-operative neuroimaging data for lumbar spine surgery patients will be split based on median baseline 2011 FM Survey Criteria score into two groups (FM-high and FM-low). Neuroimaging findings between these two groups will be compared and we hypothesize that lumbar spine surgery patients with higher preoperative 2011 FM Survey Criteria scores will have (1) *more hyperalgesia and decreased pain inhibition on QST and functional magnetic resonance imaging (fMRI)*, (2) *characteristic functional connectivity changes on fMRI (e.g., decreased functional connectivity to descending anti-nociceptive analgesic brain networks and increased connectivity to pro-nociceptive regions)*, (3) *increased CNS levels of glutamate in pro-nociceptive regions on proton spectroscopy*, and (4) *increases in S1/M1 gray matter volume*. **Analysis 3b:** We will perform whole brain analyses as per analysis 3a for all modalities with no *a priori* hypotheses to investigate the relationships between baseline imaging findings and post-surgical analgesic outcome status (AOC-success and AOC-failure) at six months.

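### Analysis 1b and its Aim 2 reuse make only the two look-alike pairings and are not tied to the failure-versus-success comparison in Analysis 1a, so on measures other than the FM score both can appear supported when outcome is unrelated to phenotype

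*Combined protocol and SAP*

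**What the plan says.** Hypothesis 1b has two limbs. Failures should resemble the established-FBSS cohort, and "those who do obtain pain relief from lumbar spine surgery will appear phenotypically similar (except for back pain) to healthy controls". Hypothesis 2b repeats the pattern for QST: "those who do obtain pain relief from lumbar spine surgery will have QST changes similar to healthy controls".

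Section II.C, Analysis 1b has one comparison per limb. For the first: "Phenotypic differences between the AOC-failure group and the established-FBSS group will be examined using appropriate parametric or non-parametric tests to see if" the two groups are alike, with the expectation "We hypothesize that AOC-failure patients will appear similar to established-FBSS patients". For the second: "The same comparisons will be explored for the longitudinally designated AOC-success group compared to the cross-sectional healthy controls group". No margin for similarity is given, and neither crossed pairing (failure versus healthy, success versus FBSS) is listed. The Aim 2 Analyses paragraph says: "The same analyses as those conducted for Aim 1 will be used for this aim".

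Analysis 1a, in the same section, does compare the outcome groups directly: "In addition to FMness, differences between AOC-success and AOC-failure groups for each of the constructs contained under the subheading" for the phenotyping battery will be examined. A stepwise logistic model follows. Through the Aim 2 sentence, both also apply to QST.

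**The concern.** Saying that failures look like FBSS tells us about surgical failure only if successes look less like FBSS. The two planned pairings cannot show that, because each outcome group is compared only with the cohort it is expected to match.

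The setting makes this a practical risk. The eligibility table requires low back pain of at least 4/10 in both the surgical and the FBSS cohorts, and QST in surgical patients is done only before surgery. Both outcome groups may therefore lie close to FBSS, or between FBSS and healthy controls. With ordinary difference tests and modest groups, non-significance on both limbs is then easy to obtain. The results are intended as the premise for a larger grant application, so a pattern reported as confirmed on this basis would carry forward.

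**Working it through.** **The plan's own figure.** Section II.C gives power only for the FM-high versus FM-low chi-squared test, 50 per group. With pooled variance and no continuity correction:

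power = Φ{[|p1 − p2| − 1.96·√(2p̄(1 − p̄)/n)] / √[(p1(1 − p1) + p2(1 − p2))/n]}

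For 0.10 versus 0.50: (0.40 − 1.96 × 0.0917)/0.0825 = 2.67, giving 0.996 (stated 0.99). The alternatives give 0.918 and 0.820 (stated 92% and 82%). The figures reproduce. None is given for Analysis 1b or its Aim 2 reuse.

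**Inputs.**
- Group sizes: all three pairs of assumed failure rates average 0.30, so about 30 failures and 70 successes among 100 patients, and 15 and 35 among the 50 with QST. FBSS and healthy cohorts have 50 each.
- Assumed, not in the documents: one measure at a time, normal, SD 1 in every group; the FBSS–healthy gap; the surgical cohort's position; no dropout.
- Null condition: failures and successes have the same distribution.
- Support is taken to mean that both pairings give p > 0.05, two-sided. The plan states no rule.

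**Formula.** The two pairings share no patients, so the joint probability is a product. For true difference δ, P(non-significant) ≈ Φ(1.96 − δ/SE) − Φ(−1.96 − δ/SE), with SE = √(1/n1 + 1/n2).

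For a 0.6 SD gap with the surgical cohort midway (δ = 0.3 on each limb):
- 30/70: failure versus FBSS, SE = √(1/30 + 1/50) = 0.231, P = 0.745. Success versus healthy, SE = √(1/70 + 1/50) = 0.185, P = 0.633. Product 0.47.
- 15/35: SEs 0.294 and 0.220, P = 0.825 and 0.725. Product 0.60.

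Simulated t-tests give 0.48 and 0.61. Simulated results for other settings:

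| FBSS–healthy gap (SD) | Surgical cohort's distance from FBSS (SD) | Both non-significant, 30/70 | Both non-significant, 15/35 |
|---|---|---|---|
| 0.6 | 0 | 0.10 | 0.22 |
| 0.6 | 0.3 (midway) | 0.48 | 0.61 |
| 0.8 | 0.3 | 0.18 | 0.32 |
| 0.8 | 0.4 (midway) | 0.26 | 0.42 |
| 1.0 | 0.3 | 0.03 | 0.10 |
| 1.0 | 0.5 (midway) | 0.10 | 0.24 |
| 1.5 | 0.75 (midway) | 0.002 | 0.02 |

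Taking 20% or 40% failures instead of 30% changes the midway results little.

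**Adding the failure-versus-success test.** Requiring it to be significant as well brings false support to at most about 3% in every setting run. At a 0.6 SD gap, midway, at least 0.48 − 0.03 = 45% of null studies (30/70) and 0.61 − 0.03 = 58% (15/35) would therefore pass both pairings beside a non-significant Analysis 1a result. The plan does not say how to read that. Requiring the two crossed pairings to be significant instead leaves up to about 10%.

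**FM score.** Healthy controls scoring above 3 are excluded, and the pilot FBSS mean was 13.7. With surgical-cohort means from 2 to 13.7 and assumed SDs of 4 to 7, both pairings passed in 0% of runs.

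**Power of the direct comparison.** The difference detectable with 80% power is (1.96 + 0.84) × √(1/n1 + 1/n2): about 0.61 SD for 30/70 and 0.87 SD for 15/35.

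**The case against.** The strongest reply is that the needed comparison is already planned. On one measure, when both outcome means lie on the same side of the FBSS mean, asking whether failures are nearer to FBSS than successes reduces to failure minus success, which is Analysis 1a, for QST as well. Hypotheses 1a and 2a carry the outcome–phenotype relation, and their results would be reported alongside. This stands: a reader might infer that the plan never tests failures against successes, and the documents contradict that. What remains is that no text makes the 1b or 2b conclusion depend on that result.

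Second, a reader might take the pass rate of the failure–FBSS pairing alone as the chance of false support. With the surgical cohort 0 to 0.3 SD from FBSS, that rate is 76–95% at n = 30. It covers one limb only; successes must also resemble healthy controls, and the closer the surgical cohort lies to FBSS, the harder that becomes. The joint figures above are the relevant ones.

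Third, the study is described as observational and hypothesis-generating, the success–healthy comparison is only to be explored, and no rule for support is written. Reading non-significance as support is therefore an inference. It is a natural one, since difference tests are to be used to judge similarity.

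An equivalence margin alone would not settle the matter. At an assumed 0.5 SD margin, with the surgical cohort 0 to 0.3 SD from FBSS, failures pass against FBSS in 18–37% of null studies and successes in 27–69%.

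**Conclusion.** The concern holds in a limited form. Analysis 1b and its Aim 2 reuse contain only the pairings expected to match, and their conclusion is not linked to Analysis 1a. The effect is material for QST and for constructs that separate FBSS from healthy controls weakly or moderately. It largely fades at gaps of 1.0 SD or more, and the FM score, the primary measure of interest, is not affected. Extending the point to that measure would go beyond the documents.

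The sizes rest on the assumed gap, common SD and position of the surgical cohort, and on 30% failures taken from the power inputs. The plan also does not state which time point supplies the surgical patients' questionnaire phenotype in Analysis 1b; QST is pre-operative only.

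**What to change.** In Analysis 1b, and explicitly for Aim 2:
- Add failure versus healthy and success versus FBSS, and report all four pairings side by side with 95% CIs.
- State that Hypothesis 1b or 2b is supported on a measure only if the failure-minus-success difference from Analysis 1a (or its Aim 2 counterpart), with its 95% CI, shows failures nearer to FBSS than successes. If the two outcome means fall on opposite sides of the FBSS mean, the sign of that difference is not enough and the two distances must be compared.
- Keep the two planned pairings as description.

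A composite score along the healthy-to-FBSS axis is optional.

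The cost is a few sentences and extra comparisons on data already being collected. The drawback is in the QST half: with about 15 failures there is 80% power only for a difference of about 0.87 SD, so Hypothesis 2b may have to be reported as inconclusive.

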Sample size for Study Procedures in Aims 1 and 2: We anticipate screening approximately 60 pre-operative lumbar spine surgery patients per year for possible enrollment into the study. Assuming a 50-60% recruitment rate, we estimate approximately 30-35 lumbar spine surgery patients enrolled per year during Years 1-4 of the award. This leads to an estimated total sample size of 100 lumbar spine surgery patients. We will also aim to recruit and enroll equal distributions of established-FBSS patients (n=50) and healthy controls (n=50). For the assumed effect size (population of 0.10 vs 0.50) and sample sizes (50 and 50 based on 2011 FM Survey Criteria score median split) and $\alpha=.05$ (two-sided) the power is 0.99. Several different assumptions were also explored. For example, if the assumed effect size is (population of 0.15 vs 0.45) or (population of 0.17 vs 0.43), then the respective power calculations are 92% and 82%, both which are adequate for significance purposes (e.g., >80%). The larger sample size will also be important for exploring multivariate models and potential subgroup analyses. The inclusion of healthy controls and established-FBSS patients will ensure adequate matching of gender and age to the patient cohorts for analyses.

Sample size for Study Procedures in Aim 3: We aim to recruit 30 lumbar spine surgery patients, 15 healthy controls, and 15 established-FBSS patients out of the total cohort to participate in the

neuroimaging study procedures. As this study is powered for the primary hypothesis in Aim 1, issues of power are of less concern for these investigatory neuroimaging studies.

D. Subject Criteria (See Vulnerable Populations appendix, if applicable):

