Participants will be recruited directly by the Candidate and by referral from specialist physicians at the KUMC [name], Comprehensive Spine and Pain Management Center. The KUMC [name], Comprehensive Spine and Pain Management Center boasts numerous faculty in various specialties such as Neurology, Anesthesiology/Pain Medicine, and Physical Medicine & Rehabilitation who can refer patients for screening into the proposed study. The Frontiers Registry and the Pioneers Community Research Recruitment services through the Frontiers: The Heartland Institute for Clinical and Translational Research will also be used to foster the recruitment of participants from the community. Both males and females will be included, and because of the potential for sex differences in pain processing, we will take care to ensure that our overall participation rate will contain relatively equal numbers of males and females in each cohort. Children under the age of 18 will be excluded from participating in this study. The rationale for this exclusion is primarily based on the fact that children in this age group rarely suffer from chronic low back pain requiring surgery or lumbar failed back surgery syndrome. In the rare cases where these surgical procedures are performed on children, the pathology is likely to be different than in adults (typically related to congenital scoliosis or other congenital spinal condition). Also, many of the measures proposed for this study are not validated in children under 18. We also will exclude individuals between the ages of 18-21 as the psychosocial circumstances of individuals under 22 are quite different from those 22 and above (i.e., educational, financial) and thus could affect study findings. Given that our study cohorts will only include patients age 22 years and older, we will not recruit any children (less than 18 years and adults between 18-21 years) as healthy controls or established-FBSS patients. No ethnic or racial groups are excluded from this protocol, nor will it involve populations that are susceptible to coercion; all subjects should be able to provide their own consent.

1. Inclusion and Exclusion Criteria for All Participants

Eligibility Criteria (All Self-Reported)

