Comprehensive Patient Phenotyping: This battery of questionnaires is intended to understand key aspects of pain, mood, and function as quickly and efficiently as possible. The focus of these measures are on obtaining an accurate assessment of pain, while also asking about physical function, anxiety, depression, and other associated somatic disturbances. [name] and other CPFRC researchers have been instrumental in developing this protocol of questionnaires. On average, the battery of questionnaires used for phenotyping take anywhere from 10 minutes to 60 minutes to complete depending on study visit.

- *Demographics:* Sex, age, race/ethnicity, marital status, education level, family history of pain, and body mass index (BMI) will be assessed in the context of standardized case report forms. Sex is an important biologic variable to investigate as centralized pain is more common in females, and is probably largely responsible for the fact that nearly any chronic pain condition is 1.5 – 2 times more common in women than in men.¹⁴²
- *Fibromyalgia-ness (FMness):* FMness is a measure of pain and co-morbid symptom extensiveness and severity. It is calculated by combining the scores from the Widespread Pain Index with the Symptom Severity Scale from the 2011 FM Survey⁶⁶ to derive a continuous metric purportedly indicative of the degree of CNS pain amplification present in a given individual.⁶⁷
- *Early Life Trauma History.* Trauma history will be assessed using The Childhood Traumatic Events Scale (CTES).¹⁴³ This scale assesses not only for physical and sexual abuse but also other

forms of early trauma such as a prolonged childhood illness, neglect, or death of a parent. Early life trauma is hypothesized to be associated with the top-down variant of centralization.

- *Clinical Pain*: Pain severity (worst, least, average, and current) due to pain will be assessed using the *Brief Pain Inventory (BPI)*. The *BPI* is validated for chronic, non-malignant forms of pain, and asks patients to rate their current pain intensity, as well as their worst, least and average pain in the 7 days (0-10 NRS) and has been recommended by IMMPACT as a measure of choice for the assessment of pain in clinical research.¹⁴⁴⁻¹⁴⁶
- *Neuropathic Pain Descriptors*: The *PainDETECT* is a 9-item measure of sensory descriptors and spatial and temporal characteristics that has demonstrated utility in identifying central neuropathic pain.¹⁴⁷

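### The within-cohort QST and imaging comparisons in Aims 2 and 3 do not pre-specify sex or age as covariates, although the protocol itself links sex to centralized pain

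*Combined protocol and SAP*

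**What the plan says.** Section II.C, Aim 2 Analyses, treats the QST measures as continuous and then states: "The same analyses as those conducted for Aim 1 will be used for this aim". The Aim 1 analyses are a chi-squared test of failure proportions by FM median split, two-group tests of each phenotyping construct between AOC-success and AOC-failure, and a stepwise logistic model. The plan lists neither the candidate variables nor any forced variables for that model.

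For Analysis 3a the surgery patients are split at the median FM score, and "Neuroimaging findings between these two groups will be compared". The hypotheses for this contrast cover QST, functional connectivity, glutamate and S1/M1 gray matter volume. Analysis 3b repeats the approach by six-month AOC status. Neither names a covariate, and the imaging methods are given by citation.

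On sex, the Demographics item of the phenotyping battery (Section II.E) says: "Sex is an important biologic variable to investigate as centralized pain is more common in females". It adds that nearly any chronic pain condition is 1.5-2 times more common in women. Section II.D says that "because of the potential for sex differences in pain processing, we will take care to ensure" roughly equal numbers of men and women in each cohort. Section II.B applies age and sex matching only to the healthy controls and the established-FBSS patients.

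**The concern.** The protocol treats sex as relevant when it recruits and matches, but does not carry it into the comparisons made inside the surgery cohort. FM-high and FM-low are formed by a median split, and the AOC groups by the six-month outcome. A cohort that is half women can still give an FM-high group with clearly more women than FM-low.

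The FM score is the protocol's surrogate for centralized pain, which it says is more common in females, and it allows that pain processing may differ by sex. Sex may therefore relate both to the grouping and to the measurement. An unadjusted difference could then partly reflect sex, or a sex effect in the other direction could hide a real difference. The results are meant as preliminary data for a larger application, so a distorted signal would be carried forward.

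**Working it through.** **The plan's own power figures.** These are stated for Aim 1 only; none is given for Aims 2 or 3. The inputs are "For the assumed effect size (population of 0.10 vs 0.50) and sample sizes (50 and 50"), two-sided 0.05. With p̄ the mean of the two proportions and n = 50 per group, power = Φ{[|p₂ − p₁| − 1.96·√(2p̄(1−p̄)/n)] / √[(p₁(1−p₁) + p₂(1−p₂))/n]}:

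- 0.10 vs 0.50: (0.400 − 0.180)/0.0825 = 2.67, power 0.996 (stated 0.99)
- 0.15 vs 0.45: (0.300 − 0.180)/0.0866 = 1.39, power 0.918
- 0.17 vs 0.43: (0.260 − 0.180)/0.0879 = 0.91, power 0.820

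For the last two the plan says "then the respective power calculations are 92% and 82"%. The figures reproduce. What matters here is the failure rate they imply: (0.10 + 0.50)/2 = 30%.

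**Group sizes.** Aim 2 has 50 surgery patients with QST, so about 0.30 × 50 = 15 AOC-failure and 35 AOC-success. Aim 3 has 30 surgery patients, so 15 vs 15 after the median split and about 9 vs 21 by AOC.

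**Sex imbalance.** Assume equal numbers of men and women, and apply the ratio k = 1.5 to 2 to being FM-high. The share of women is k/(1+k) in FM-high and 1/(1+k) in FM-low.

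- k = 1.5: 60% vs 40%, gap 20 points
- k = 2: 67% vs 33%, gap 33 points

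Next, pass this through the 0.50 and 0.10 failure rates.

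- k = 1.5: P(failure) is 0.5×0.6 + 0.1×0.4 = 0.34 in women and 0.26 in men. Women are 0.34/0.60 = 57% of failures and 0.66/1.40 = 47% of successes, gap 9.5 points.
- k = 2: the probabilities are 0.367 and 0.233. Women are 61% of failures and 45% of successes, gap 16 points.

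**Bias.** Bias = sex effect × gap. The documents give no sex effect, so 0.3-0.8 SD is assumed.

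- Analysis 3a: 0.3 × 0.20 = 0.06 SD to 0.8 × 0.333 = 0.27 SD
- Aim 2 by AOC: 0.3 × 0.095 = 0.03 SD to 0.8 × 0.159 = 0.13 SD

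The AOC bias applies equally to Analysis 3b, because it does not depend on sample size. False-positive rates were not computed for 3b.

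**False positives.** Simulated with no true group difference, within-sex SD 1, nominal 5% and 6,000 runs per case (Monte Carlo standard error √(0.05×0.95/6000) = 0.3 points). The test is an unadjusted t-test.

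| Sex effect | 3a, k = 1.5 | 3a, k = 2 | Aim 2 AOC, k = 1.5 | Aim 2 AOC, k = 2 |
|---|---|---|---|---|
| 0.3 SD | 5.4% | 5.6% | 5.1% | 5.1% |
| 0.5 SD | 5.8% | 6.9% | 4.7% | 5.2% |
| 0.8 SD | 6.6% | 10.6% | 5.3% | 6.7% |

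If the ratio is applied directly to failure instead, the AOC gap is 14-24 points, bias reaches 0.8 × 0.238 = 0.19 SD and false positives reach 8.5%. With sex in a linear model, bias is about zero and the rate is 4.5-5.5% throughout.

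**Masking.** In Analysis 3a, assume a true difference of 0.8 SD and a sex effect in the opposite direction. Unadjusted power runs from 0.50 (0.3 SD, k = 1.5) down to 0.25 (0.8 SD, k = 2). With sex in the model it is 0.48-0.54.

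Age could not be quantified, because the documents give no age effect.

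**The case against.** Sex and age are not absent from the plan. Both belong to the Demographics item of the battery whose constructs are compared between AOC groups, so an imbalance there may be seen. Both may also be candidates in the stepwise model that Aim 2 inherits. This stands, and it rules out saying that the plan includes neither. However, comparing sex between groups does not adjust the QST comparison for it, and a stepwise model with about 15 failures can drop a confounder.

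An unadjusted association is a legitimate target. Hypothesis 2a asks about association and possible prediction, and greater centralized pain in women may be part of the phenomenon. This also stands, and is the reason to report both versions.

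For Aim 3, the methods are cited and their covariates cannot be checked. The title of one cited gray-matter study refers to age matching and to control for affective disorder. Adjustment there is unstated, not shown to be missing. Aim 3 is also declared exploratory and possibly underpowered.

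The 1.5-2 ratio describes chronic pain conditions in general. It is not the chance of being FM-high among patients who all have back pain of at least 4/10 and are due for surgery. Every magnitude above depends on that transfer.

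A reader might also apply the FM split to all 50 QST patients (25 vs 25), where false positives run from 5% to 14%. Aim 2 does not specify that contrast; QST by FM group appears only in Analysis 3a.

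**Conclusion.** The concern holds as a gap in pre-specification. No QST or imaging comparison inside the surgery cohort fixes sex or age as a covariate, and neither the matching nor the balanced recruitment covers these groups. Under the stated assumptions the distortion is small for the Aim 2 AOC contrast (0.03-0.13 SD, 5-7% false positives, 8.5% at most). It is moderate for Analysis 3a (0.06-0.27 SD, 5-11%), where an opposing sex effect could roughly halve power.

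These sizes rest on an assumed sex effect of 0.3-0.8 SD, the transferred ratio, equal numbers of men and women, 30% failure and no dropout.

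A reader might infer that sex differences will be mistaken for central amplification, or that the study cannot separate the two. The documents do not support that: they give no size for a sex effect, and both variables are collected and can be added. Nor do they state any sex or age difference in brain volume, so no claim is made about the S1/M1 result in particular. The relevance of age is implied only by the matching. The change is worth making because it is nearly free, not because the planned contrasts are invalid.

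**What to change.** In Section II.C, for Aim 2 and Analyses 3a and 3b, specify a linear model for each QST or imaging measure (rank-transformed if needed). The predictors are AOC group or FM score, with sex and age always included. Report the unadjusted contrast beside it, and tabulate sex and age by FM group and by AOC group. Making the measurement the outcome is also more stable than a logistic model with several terms and about 15 failures. For Aim 3, state in the plan which covariates are used, so that this does not depend on cited papers.

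The cost is a few sentences of plan wording and two degrees of freedom out of 30-50. Both variables are already collected.
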